3.2.2 Secondary Endpoints

The secondary endpoints are:

- Analysis of ABI-H2158 and ETV drug concentrations:
 - Trough levels and trough to peak ratios of ABI-H2158 on ABI-H2158+ETV
 - Trough levels and trough to peak ratios of ETV on ABI-H2158+ETV and PBO+ETV
- The change in mean log₁₀ HBV DNA for ABI-H2158+ETV and PBO+ETV at each timepoint
- The change in mean log₁₀ HBV pgRNA from Baseline to Week 24 and at each timepoint for ABI-H2158+ETV and PBO+ETV
- The proportion of subjects with a reduction in HBV DNA below the assay lower limit of quantitation (LLOQ) for ABI-H2158+ETV and PBO+ETV at each timepoint
- The proportion of subjects with a reduction in HBV pgRNA below the assay LLOQ for ABI-H2158+ETV and PBO+ETV at each timepoint
- The change in serum viral antigens (ie, HBeAg, HBcrAg, and HBsAg) on ABI-H2158+ETV and PBO+ETV at each timepoint
- The proportion of subjects with abnormal ALT at Baseline who have normal ALT at Week 24 and at each timepoint on ABI-H2158+ETV and PBO+ETV
- The incidence of HBV variants with reduced susceptibility to ABI-H2158

3.2.3 Exploratory Endpoints

Exploratory endpoints will include:

- The proportion subjects with loss (defined as below LLOQ) or decline in HBsAg, HBcrAg, HBeAg or new biomarkers on ABI-2158+ETV and PBO+ETV at each timepoint
- The proportion of subjects with HBsAg seroconversion (loss of HBsAg and appearance of HBsAb) or HBeAg seroconversion (loss of HBeAg and appearance of HBeAb) on ABI-H2158+ETV and PBO+ETV at each timepoint for applicable cohort
- The proportion of subjects whose HBV DNA is below the assay LLOQ and “target not detected” on ABI-H2158+ETV and PBO+ETV at each timepoint
- Pharmacogenomic correlations may be performed with clinical or virologic outcomes for subjects who provide an additional informed consent. Known gene variants and PK and/or safety of ABI-H2158 and its metabolites may be evaluated

4 STUDY PLAN

4.1 Study Design

This Phase 2a, multicenter, randomized, single-blind (ie, investigational site and subjects are blinded), PBO-controlled study will assess the safety, antiviral activity, and PK of ABI-H2158 administered QD in combination with ETV in subjects with CHB. It is planned that multiple parallel cohorts will be enrolled in the study.

[figure not shown]
The first treatment cohort will evaluate ABI-H2158 300 mg in combination with ETV (n=30) compared to ETV alone (n=10) in treatment-naïve subjects with HBeAg positive CHB. The second treatment cohort will evaluate ABI-H2158 300 mg in combination with ETV (n=30) compared to ETV alone (n=10) in treatment-naïve subjects with HBeAg negative CHB. Additional cohorts may be added by future protocol amendment(s) based, in part, upon emergent safety, antiviral activity, and PK data from the ABI-H2158 regimens evaluated in the ongoing Phase 1b study ABI-H2158-101 ([Section 2.2.3.1](#)).

In Cohort 1, subjects will be randomized in a 3:1 ratio to receive 300 mg ABI-H2158+ETV (n=30) or matching PBO+ETV (n=10) for 72 weeks ([Figure 1](#)). Treatment assignments will be stratified by the HBV DNA level measured at the Screening visit (ie, $\geq 8.0 \log_{10}$ IU/mL versus $< 8.0 \log_{10}$ IU/mL). After completing treatment at Week 72, or following premature treatment discontinuation, all subjects will enter a 24-week follow-up period. During the follow-up period all subjects will remain on ETV and undergo the follow-up assessments described in [Section 7.5](#). After completing the 24-week follow-up period, all subjects will resume management by their treating physician in accordance with local standard of care.

In Cohort 2, subjects will be randomized in a 3:1 ratio to receive 300 mg ABI-H2158+ETV (n=30) or matching PBO+ETV (n=10) for 72 weeks ([Figure 1](#)). Treatment assignments will be stratified by the HBV DNA level measured at the Screening visit (ie, $\geq 6.0 \log_{10}$ IU/mL versus $< 6.0 \log_{10}$ IU/mL). After completing treatment at Week 72, or following premature treatment discontinuation, all subjects will enter a 24-week follow-up period. During the follow-up period all subjects will remain on ETV and undergo the follow-up assessments described in [Section 7.5](#). After completing the 24-week follow-up period, all subjects will resume management by their treating physician in accordance with local standard of care.

Additional cohort may be added to this study by future protocol amendment(s) in order to evaluate other doses of ABI-H2158, other ABI-H2158-containing regimens, and/or other subgroups of patients with CHB.

Figure 1: Study Overview

PBO: placebo; ETV: entecavir; HBeAg: hepatitis B “e” antigen; NrtI: nucleos(t)ide reverse transcriptase inhibitor of the hepatitis B virus polymerase.

The schedule of study procedures is described in [Section 7](#) and presented in tabular form in [Appendix 1](#). In addition to the routine medical oversight of the study, safety will also be closely monitored by an internal Data Review Committee (DRC). The team membership, roles and responsibilities and the frequency of analyses will be specified within the DRC Charter.

An assessment of PK data will be performed after all subjects in each cohort have completed their Week 4 study visit (or discontinued study without completing Week 4) in order to confirm the absence of important drug interactions between ABI-H2158 and ETV at steady state. A detailed review of the planned PK analyses in this study is provided in [Section 7.8.8](#).

4.2 Dose Justification

In the ongoing Phase 1a/b clinical study ABI-H2158-101 ([Section 2.2.3.1](#)), single ABI-H2158 doses of 5 mg, 25 mg, 100 mg, and 300 mg QD were administered to healthy subjects (6 active, 2 PBO per dose level). Following completion of the SAD assessment, ABI-H2158 was subsequently administered as 300 mg QD to healthy subjects for 10 days (6 active, 2 PBO). Finally, in treatment-naïve subjects with HBeAg positive CHB, ABI-H2158 100 mg and 300 mg (7 active, 2 PBO per dose level) was administered once daily for 14 days. No safety signals have been observed in a cumulative data analysis. All dose levels were well tolerated and no subject prematurely discontinued treatment due to AEs. There were no Grade 3 or 4 AEs or SAEs. Treatment-emergent AEs did not increase in frequency or severity with either dose or duration. All treatment-emergent laboratory abnormalities were Grade 1 or Grade 2. Preliminary data indicates that there is a dose-dependent decrease in HBV DNA at doses of 100 mg and 300 mg daily in subjects with CHB ([Section 2.3](#)). The results of the following doses of ABI-H2158 (500 mg QD and 300 mg BID) for 14 days is described in the current version of the ABI-H2158 IB.

Interim analysis indicates exposures in the 100 mg and 300 mg CHB patient cohorts are similar to exposures in healthy volunteers. Mean Day 14 C_{max} values in the 100 mg and 300 mg CHB cohorts are 3390 and 8400 ng/mL, respectively, and mean Day 14 AUC_{0-24} are 46,100 and 112,000 ng*hr/mL, respectively.

It is anticipated that the 300 mg QD regimen will be safe and provide sufficient ABI-H2158 exposure to evaluate the antiviral effect in CHB subjects in this study, and within the dose range that has been well tolerated in healthy volunteers and subjects with CHB to date.

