Non-adverse ABI-H2158-related effects on serum chemistry parameters were limited to slightly lower serum lactate dehydrogenase (LDH) levels for the Group 2-4 males and females throughout the dosing period. Mean LDH values were comparable to control group values by the end of the recovery period. The LDH changes were not considered adverse due to the low magnitude, lack of microscopic correlates and reversibility.

Once daily oral (gavage) administration of ABI-H2158 to male and female Cynomolgus monkeys at dose levels of 0, 20/15, 60/30 or 120 mg/kg/day for 273 consecutive days was well tolerated. Non-adverse, ABI-H2158-related findings were limited to increased incidence of non-severe hair loss for the 60/30 and 120 mg/kg/day males, slightly lower body weights for the 60/30 and 120 mg/kg/day females vs controls, and lower serum lactate dehydrogenase levels for all ABI-H2158-treated male and female groups. Following daily oral doses for 9-months, the NOAEL for ABI-H2158 was considered to be 120 mg/kg/day for male and female Cynomolgus monkeys, a dose level yielding Day 273 mean plasma C_{max} of 14.4-19.8 $\mu\text{g/mL}$ (average 17.1 $\mu\text{g/mL}$) and AUC_{0-24} of 182-223 $\text{hr}*\mu\text{g/mL}$ (average of 203 $\text{hr}*\mu\text{g/mL}$). These exposures are approximately twice the average exposures at the NOAEL dose in the 14-day monkey study (C_{max} of 9.6 $\mu\text{g/mL}$ and AUC_{0-24} of 86.6 $\text{hr}*\mu\text{g/mL}$), and approximately 20%-25% of the exposure levels that caused acute liver toxicity and morbidity at the 100 mg dose in the 14-day monkey study (C_{max} and AUC_{0-24} of 62.6 $\mu\text{g/mL}$ and 1,035 $\text{hr}*\mu\text{g/mL}$).

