Interim PK estimates of AUC and C_{max} of ABI-H2158 were analyzed using analysis of variance with sequence, period, and treatment as fixed effects and subject within sequence as the random effect on naturally logarithmic-transformed values. Geometric least squares mean ratios of the 300 mg reference group (12 x 25 mg tablets) relative to the 300 mg test group (3 x 100 mg tablet) for C_{max} and AUC from time 0 extrapolated to infinity (AUC_{0-inf}) are 94.9 (100,600 and 106,000 ng/mL, respectively) and 80.4 (4720 and 5870 ng*hr/mL, respectively). Exposures after administration of the 300 mg test (3 x 100 mg tablets) in the fed state after a high-fat meal increased approximately 40% as measured by AUC_{0-inf} (143,000 ng*hr/mL) and approximately 30% for C_{max} (6160 ng/mL).

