2.3 Study Rationale

Current approved therapies are generally safe, well tolerated and effective at suppressing viral replication in most patients but do not eliminate viral replication and SVR is rare. Novel therapeutic modalities are required to improve chronic suppressive regimens and support finite duration therapy. The HBV Cp is involved in multiple steps in the HBV life cycle, including both viral replication and the establishment of new cccDNA (Levrero 2009, Belloni 2013). Inhibition of HBV Cp represents a novel therapeutic strategy for the treatment of CHB (Yang 2019). Interim analyses of Phase 2a studies, demonstrated subjects treated with the first-generation CI ABI-H0731 with a NrtI compared to those treated with NrtI alone achieved faster and deeper declines in HBV DNA and in HBV pgRNA, a surrogate marker of cccDNA. In these studies, the observed declines in HBV pgRNA correlated with reductions in HBeAg, HBcrAg, and HBsAg (Sulkowski 2019).

ABI-H2158 is a second-generation CI being developed by Assembly Biosciences. In vitro, ABI-H2158 has demonstrated potent antiviral activity as measured by inhibition of HBV DNA with a 50% effective concentration (EC_{50}) of 22 nM in HepAD38 cells and 41 nM in primary human hepatocytes (PHH). In the PHH infected cells, the EC_{50} s for inhibition of HBV pgRNA, HBeAg, and HBsAg production were 216 nM, 204 nM, and 160 nM, respectively. ABI-H2158 is currently being evaluated as monotherapy in a Phase 1b clinical study (ABI-H2158-101) in treatment-naïve subjects with HBeAg positive CHB (Section 2.2.3.1). In the initial dose group tested (100 mg ABI-H2158 QD), the mean declines in HBV DNA and HBV pgRNA from Baseline to Day 15 were 2.3 \log_{10} IU/mL (range 1.7, -3.0) and 2.1 \log_{10} IU/mL (range 1.5, -2.7), respectively. At the 300 mg QD dose level, the mean declines in HBV DNA and HBV pgRNA from Baseline to Day 15 were 2.5 \log_{10} IU/mL (range 0.8, -3.3) and 2.12 \log_{10} IU/mL (range 1.4, 2.6). At this time, a third dose group evaluating ABI-H2158 500 mg QD is currently ongoing.

Based on these data, the addition of ABI-H2158 to NrtI therapy may improve treatment responses compared with NrtI alone. It is anticipated that the addition of ABI-H2158 to entecavir (ETV) will be well tolerated and increase the rate and extent of decline in HBV DNA and HBV pgRNA. Furthermore,

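### Does the dose justification in Protocol Section 4.2 misstate the Phase 1 data in a way that calls for a change to the plan?

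*Combined protocol and SAP*

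**What the plan says.** Section 4.2 makes three statements about earlier data before concluding "It is anticipated that the 300 mg QD regimen will be safe".

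- Laboratory safety in Study 101: "All treatment-emergent laboratory abnormalities were Grade 1 or Grade 2".
- Exposure: "Interim analysis indicates exposures in the 100 mg and 300 mg CHB patient cohorts are similar to exposures in healthy volunteers". It then gives Day 14 means in CHB subjects at 100 and 300 mg: Cmax 3390 and 8400 ng/mL, and AUC0-24 "46,100 and 112,000 ng*hr/mL". It does not say which healthy data were used or whether the means are arithmetic or geometric.
- Antiviral effect: "Preliminary data indicates that there is a dose-dependent decrease in HBV DNA at doses of 100 mg and 300 mg daily".

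The figures behind these statements are in Section 2. Section 2.2.3.1.4 and Table 4 give the laboratory grades. Tables 1 and 2 and Section 2.2.3.2 give pharmacokinetics in healthy subjects. Section 2.3 gives the antiviral results: "At the 300 mg QD dose level, the mean declines in HBV DNA and HBV pgRNA from Baseline to Day 15 were 2.5" and 2.12 log10 respectively, against 2.3 and 2.1 at 100 mg.

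**The concern.** Read side by side, Section 4.2 and Section 2 do not agree. Table 4 counts abnormalities that worsened from baseline and shows a Grade 3 cholesterol that Section 4.2 says did not occur. Table 2 is the only multiple-dose healthy data printed, from the same study and the same 300 mg daily regimen, and its exposures are about half those quoted for CHB subjects. The HBV DNA means at the two doses differ by only 0.2 log10, and the smallest individual decline (0.8) was at 300 mg.

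Each statement leans towards reassurance about a regimen to be given to 60 subjects for 72 weeks. The SAP Introduction records that development stopped after ALT elevations consistent with drug-induced liver injury. If the rationale had rested on wrong figures, readers of the final report could be misled about prior safety and about how far patient exposure lay from the animal exposures.

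**Working it through.** **1. Laboratory grades.** Section 2.2.3.1.4 is coherent with its tables: any graded abnormality (7 + 5)/14 = 86%, ALT (2 + 2)/14 = 29%, adverse events (3 + 2)/14 = 36%, all as printed. The Section 4.2 sentence is therefore the outlier. The missed event is 1/14 = 7.1% (exact 95% interval 0.2% to 33.9%). It was at 100 mg and was not reported as an adverse event, so the neighbouring statement that Study 101 had no Grade 3 or 4 adverse events remains correct.

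**2. Exposure.** AUC in hr·µg/mL. Single-dose AUC0-inf may be set against steady-state AUC0-24 only if the pharmacokinetics are linear and do not change with time, as Sections 2.2.3.1.2 and 2.2.3.1.3 suggest. The feeding state of the CHB cohorts is not given.

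| Healthy comparator | Healthy | CHB | Ratio |
|---|---|---|---|
| Study 101, 300 mg daily, Day 10 (geometric mean) | 55.1 | 112 | 2.03 |
| Same, converted to arithmetic: 55.1 × √(1 + 1.02²) | 78.7 | 112 | 1.42 |
| Study 101, single 300 mg fasting, AUC0-inf | 65.0 | 112 | 1.72 |
| Study 101, single 100 mg fasting, AUC0-inf | 31.8 | 46.1 | 1.45 |
| Study 101, single 100 mg fed, AUC0-inf | 37.5 | 46.1 | 1.23 |
| Study 102, single 300 mg fasting, AUC0-inf | 100.6 to 106 | 112 | 1.11 to 1.06 |
| Study 102, single 300 mg fed, AUC0-inf | 143 | 112 | 0.78 |

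For Cmax, Table 2 gives 8.40/4.21 = 2.00. Study 102, with the accumulation of 1.5 from Table 2, gives 8400/(5870 × 1.5) = 0.95 or 8400/(4720 × 1.5) = 1.19.

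**3. Precision of the largest AUC ratio.** The healthy log-scale SD is √ln(1 + 1.02²) = 0.844, n = 6. The CHB CV is not given; at an assumed 36% the log SD is √ln(1 + 0.36²) = 0.349, n = 7. The standard error is √(0.844²/6 + 0.349²/7) = 0.369. With Welch degrees of freedom the 95% interval for 2.03 is about 0.84 to 4.9. An assumed CV of 20% gives 0.84 to 4.9, and 102% gives 0.72 to 5.7. The interval includes 1, and it also includes a difference of more than fourfold.

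**4. Study 102 as printed.** The text reads "94.9 (100,600 and 106,000 ng/mL, respectively) and 80.4 (4720 and 5870 ng*hr/mL, respectively". The ratios reproduce: 100,600/106,000 = 94.9% and 4720/5870 = 80.4%. The magnitudes show that the Cmax and AUC labels and units are transposed. The two tablet arms may be swapped as well. The stated fed increases for the test tablet, about 40% (to 143,000) and 30% (to 6160), fit 143,000/100,600 = 1.42 and 6160/4720 = 1.31. They fit less well with 143,000/106,000 = 1.35 and 6160/5870 = 1.05. Either arm gives an AUC ratio close to 1.

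**5. HBV DNA.** Section 2.3 gives means of 2.3 (range read as 1.7 to 3.0) and 2.5 (0.8 to 3.3), with 7 active subjects each. Estimating each SD as range/2.704 gives 0.48 and 0.92; SE = √((0.48² + 0.92²)/7) = 0.39; difference 0.2, 95% interval −0.69 to 1.09. With the smallest SDs that the means and ranges allow (0.38 and 0.78) the interval is −0.52 to 0.92. The data cannot establish a dose response, but the means are in the stated order, and the largest decline (3.3) was also at 300 mg.

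**6. What depends on these statements.** Protocol 10.2 says the sample size has no statistical basis. The ANCOVA (SAP 6.1.2) uses only this trial's data. Laboratory results are graded from this trial's values under Appendix 2 (SAP 7.2.1), and the ALT rules in Protocol 9.4 use multiples of baseline and the upper limit of normal. None takes an input from Section 4.2.

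**The case for a change.** The strongest argument for acting is that the comparator changes the margin a reader would derive. In Section 2.2.2.2, "Following daily oral doses for 9-months, the NOAEL for ABI-H2158 was considered to be 120 mg/kg/day for male and female Cynomolgus monkeys", with AUC 203 and Cmax 17.1. On the CHB figures the ratios are 203/112 = 1.8 and 17.1/8.40 = 2.0; on the Table 2 figures they are 203/55.1 = 3.7 and 17.1/4.21 = 4.1. Calling the two populations similar could let a reader adopt the larger margin. SAP 6.2 also drops the secondary endpoints, and SAP 3.1 has no pharmacokinetic set, so patient exposure from this trial may go unreported.

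The difference in margin is real, but Section 4.2 states no margin. It prints the CHB exposures directly after the word similar, and those give the smaller, more cautious ratio. The suggestion of slant is also weak. Section 4.2 leaves out the completed 500 mg single-dose cohort (Section 2.2.3.1), which would have helped its case, and it refers to the Investigator's Brochure for 14-day results at higher daily doses. That pattern looks like untidy updating.

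A descriptive pharmacokinetic table would not settle the exposure question. Protocol Table 6 schedules predose samples at Weeks 4, 48 and 72 and single postdose windows at other weeks. No scheduled steady-state visit pairs a trough with a peak, so the table could not yield an AUC0-24, or a Cmax comparable with 8400 ng/mL. A population model might, but neither document describes one.

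Three things stand: the laboratory sentence is wrong, the Study 102 labels are transposed, and the comparator and type of mean are not named.

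**Conclusion.** No change to the plan follows. The one firm contradiction is the laboratory sentence, which omits 1 event in 14 subjects; it and the Study 102 labels must be reconciled with their sources wherever the text is reused, which is a clerical correction. The exposure statement is under-referenced rather than contradicted: AUC ratios run from 0.78 to 2.03 depending on comparator, and the largest is imprecise. The dose-dependence remark is stronger than 7 subjects per dose can bear, but it is labelled preliminary and agrees with the means.

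This rests on linear pharmacokinetics for the single-dose comparisons, on reading the Study 102 values by magnitude, on an assumed CHB CV for the interval, and on SDs inferred from ranges. The conclusion is insensitive to these assumptions, because no sample size, analysis or decision rule in the protocol or SAP draws on the three statements. Neither document says that Section 4.2 will be carried into the Synoptic CSR. No view is taken on which dose is right.

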4.3 Study Treatment

This study is designed to evaluate the safety, PK, and antiviral activity of various ABI-H2158-containing regimens in subjects with CHB. These regimens will be evaluated in multiple treatment cohorts. Cohort 1 will enroll treatment-naïve subjects with HBeAg positive CHB and Cohort 2 will enroll treatment-naïve subjects with HBeAg negative CHB.

The study treatment (ABI-H2158 or PBO) will be administered in combination with a standard-of-care known effective therapy (ETV). All subjects will receive ABI-H2158 or matching PBO as three 100 mg tablets QD. ETV will be administered as a single 0.5 mg tablet QD. ABI-H2158, matching PBO, and ETV will be administered on an empty stomach (at least 2 hours after a meal and 2 hours before the next meal) at approximately the same time each day. Further information is provided in the ETV package insert. On study visit days, ABI-H2158 or PBO will be administered in the clinic; subjects will self-administer assigned treatment on all other days. On study visit days which include PK collection ([Section 7](#)), subjects will administer ABI-H2158 or PBO and ETV in the clinic except for Week 16 and Week 20. Study personnel will document the time of study drug administration in the subject's medical record. Subjects will be required to record the dates and times of each dose of study drug (ie, ABI-H2158 or PBO and ETV) they self-administer in the dosing diary provided to them at the Day 1 visit.

4.4 Duration of Treatment

All subjects will receive their randomized treatment assignment in a blinded manner for up to 72 weeks. After completing treatment at Week 72, or following premature treatment discontinuation, all subjects will enter a 24-week follow-up period. During the follow-up period all subjects will remain on ETV and undergo the follow-up assessments described in [Section 7.5](#). After completing the 24-week follow-up period, all subjects will resume management by their treating physician in accordance with local standard of care.

5 POPULATION

5.1 Number of Subjects

A total of approximately 80 subjects (40 subjects per Cohorts 1 and 2) are planned.

5.2 Inclusion Criteria

Subjects must meet **all** of the following inclusion criteria in order to be eligible for the study:

1. Willing and able to provide informed consent
 2. Male or female between the ages 18 and 65 years (inclusive)
 3. Female subjects must be non-pregnant and have a negative serum pregnancy test at Screening and a negative urine pregnancy test predose on Day 1
 4. Chronic HBV infection, defined as HBV infection for ≥ 6 months documented, for example, by at least two measurements of HBsAg positivity and/or detectable HBV DNA ≥ 6 months apart (inclusive of Screening). For subjects without clear documentation of CHB, anti-hepatitis B core antigen immunoglobulin M (IgM) antibody to the HBV core antigen (HBcAb) must be negative at Screening to exclude acute HBV infection
 5. Body mass index (BMI) 18 to 36 kg/m² and a minimum body weight of 45 kg (inclusive)
 6. HBV DNA $\geq 2 \times 10^5$ IU/mL for subjects who are treatment naïve HBeAg positive
 7. HBV DNA $\geq 2 \times 10^3$ IU/mL for subjects who are treatment naïve HBeAg negative
 8. HBsAg > 1000 IU/mL at Screening for subjects who are treatment naïve HBeAg positive
 9. Lack of cirrhosis or advanced liver disease as documented by the following:
 - Liver biopsy results of METAVIR F0-F2 (absence of bridging fibrosis or cirrhosis) within 1 year of Screening
- OR**
- Fasting FibroScan ≤ 8 kPa within 3 months of Screening (including Screening visit) or other Sponsor-approved hepatic imaging study (hepatic magnetic resonance elastography [MRE]) within 6 months of Screening indicating lack of cirrhosis or advanced liver disease (F0-F2 or equivalent)

Subjects with a fasting FibroScan > 8 kPa and ≤ 10 kPa are excluded from study participation unless a liver biopsy within the 1 year before Day 1 confirms the absence of bridging fibrosis and cirrhosis. Subjects with a FibroScan > 10 kPa are excluded from study participation

If results from both liver biopsy and FibroScan are available, then the result reporting the most advanced liver disease will be used to determine eligibility for the study

10. Agreement to comply with protocol-specified contraceptive requirements (Refer to [Appendix 3](#))
11. Agreement to abstain from alcohol abuse [defined as alcohol consumption exceeding 2 standard drinks per day on average (1 standard drink = 10 grams of alcohol)] and the use of illicit substances from screening until end of the study
12. In good general health, except for CHB
13. Have the ability to take oral medication and, in the opinion of the Investigator, be willing to adhere to study treatment
14. Candidate for treatment with ETV and have no contraindications as described in the approved product labelling

